4.2 Study Enrollment Procedures

Patients will be approached for enrollment in this study prior to surgery. Some patients may be called by research staff to describe the study and assess their willingness to participate if time allows based on the surgery schedule. The consent process will be conducted with the patient by an IRB-approved consent designee that is also a physician or a mid-level provider prior to surgery. As part of the consent process, the investigator or study team members will have 1) informed each patient accordingly and allowed sufficient time to decide whether or not to participate in the study; and 2) given the opportunity to inquire about details of the study and to answer any questions regarding the study. Patients are free to withdraw consent for participation in the study at any time, without prejudice to further treatment. A patient's participation in the study may be discontinued at any time at the discretion of the PI.

If the patient is not signing consent for surgery and has a medical decision maker doing so, then it will be determined that this patient lacks the capacity to give written consent for this project. Of note, we are excluding patients with known dementia. We will identify the legally authorized representative in accordance with the Maryland law applicable to surrogate decision-making for health care to sign written consent. If the patient regains the capacity to consent, signs their own consents, and no longer requires a medical decision maker, then we will discuss this project with them and confirm their willingness to participate. We will attempt to discuss the study with patients who do not sign their own consents due to lack of capacity. However, we anticipate that the cognitive capacity of these patients will be low and they may not be able to understand. Thus, we will not obtain formal assent.

FEAT Study Protocol

5. STUDY PROCEDURES

5.1. Schedule of Evaluations

Name	HOSPITALIZATION PHASE								FOLLOW-UP PHASE (± 30 days)		
	Screening	Baseline	Day of Surgery	Intraop monitoring	POD 1	POD 2	POD 3	Post Discharge	Day 60	Day 180	Day 365
Demography	✓										
Registration and Contact		✓									
Short Blessed Test		✓									
AD8 (patient or proxy)		✓									
Eligibility Confirmation		✓									
Baseline Exam (Pain scales, OTMT, WHO-DAS 2.0, IADL, BRS, 3D-CAM)		✓									
NIRS Monitoring			✓	✓							
Clearsight or arterial monitoring			✓	✓							
BIS monitoring			✓	✓							
Randomization and Intervention			✓	✓							
Surgery Data Collection									✓		
Postoperative Assessment (3D-CAM, Pain, Adverse Events)					✓	✓	✓				
Discharge Contact Info								✓			
Postoperative Events (Pain, Discharge contact)									✓		
Follow-up (Patient or Proxy) (60, 180, 365 days)									✓	✓	✓
AD8 (Patient or Proxy; 365 days)											✓
Adverse Events			✓		✓	✓	✓	✓	✓	✓	✓
End of Study											✓

¹WHODAS or WHODAS-Proxy to be used as appropriate.

FEAT Study Protocol

5.2.2 Enrollment

Prior to the start of surgery, the patient will be enrolled in the study. At this time, the patient will be assigned a study number. During the study patients will be identified by their first and last initial and a unique study number.

Patients who are excluded based on the secondary screen (Short Blessed Test) or for other reasons (e.g. cancelled surgery) will retain a study number but will be noted to be excluded or withdrawn, as appropriate, prior to randomization.

Study numbers will be assigned sequentially, starting with 3001.

5.2.3 Baseline Data

The following data will be collected onto case report forms (CRFs)

- Participant ID/Screening
- Registration and Contact Information
- Eligibility Confirmation
- Baseline Exam
- Baseline Pain Assessment
- 3D CAM
- Short Blessed Test
- Oral Trail Making Test
- AD8 (patient or proxy)
- WHODAS (or WHODAS Proxy)
- Instrumental Activities of Daily Living
- Brief Resilience Scale

FEAT Study Protocol

5.2.4 Intraoperative Data

Surgical and anesthesia characteristics will be extracted from EPIC and/or the anesthesia monitor.

All subjects may be monitored during surgery using the following devices:

- **Near Infra-red Spectroscopy** is an FDA noninvasive device that is routinely used to monitor cerebral oxygen saturation during cardiac surgery. It is applied as adhesive pads to the forehead and is routinely used in cardiac surgery.
- The **Clearsight monitor** is FDA noninvasive device that is used to monitor arterial blood pressure waveforms during surgery. It is applied as a device around the finger.
- The **Bispectral Index** is an FDA noninvasive processed EEG that is used in clinical care to measure depth of anesthesia. It is applied as an adhesive patch to the forehead.

5.2.5 Postoperative Data

The following assessments will be performed and entered in CRFs

Post-op Day #1

- 3D CAM (CAM-ICU for intubated patients)
- Post-op Assessment
- Pain Scales – Post-op
- Adverse Events

Post-op Day #2

- 3D CAM (CAM-ICU for intubated patients)
- Post-op Assessment
- Pain Scales – Post-op
- Adverse Events

Post-op Day #3

- 3D CAM (CAM-ICU for intubated patients)
- Post-op Assessment
- Pain Scales – Post-op
- Adverse Events

Discharge

- Surgery Data Collection
- Postoperative Events
- Adverse Events
- Acute Pain Management
- Discharge Contact Information

Day 60

- Ambulation
- Adverse events
- Pain
- Short Blessed Test
- Oral Trail Making Test
- WHODAS (or WHODAS Proxy)
- Instrumental Activities of Daily Living

FEAT Study Protocol

Day 180

- Ambulation
- Adverse events
- Pain
- Short Blessed Test
- Oral Trail Making Test
- WHODAS (or WHODAS Proxy)
- Instrumental Activities of Daily Living

Day 365

- Ambulation
- Adverse events
- Pain
- Short Blessed Test
- Oral Trail Making Test
- AD8 (patient or proxy)
- WHODAS (or WHODAS Proxy)
- Instrumental Activities of Daily Living

End of Study

- The End of Study form will be filled out at the time the participant completes the study or ends participation early.

5.3 Randomization

Randomization will be 2:1 in intervention vs. standard arm with stratification by orthopedic vs. lung surgery in permuted blocks of 3 or 6 (i.e. each surgical strata will have the opportunity for 17 intervention patients and 8 control patients to be enrolled). A patient will be considered to be randomized when they enter the operating room and the anesthesiologist is handed a sealed opaque envelope indicating the study allocation.

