3 STUDY DESIGN

3.1 Study Design Overview

We will conduct a randomized, double-masked controlled trial. We will enroll 25 patients with usable data. Randomization will be 2:1 in intervention vs. standard arm with stratification by orthopedic vs. lung surgery in permuted blocks of 3 or 6 (i.e. each surgical strata will have the opportunity for 17 intervention patients and 8 control patients to be enrolled).

Patients randomized to the intervention arm will have their MAP targeted within the limits of cerebral autoregulation during surgery. Patients randomized to the standard arm will receive observational monitoring.

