4. SELECTION AND ENROLLMENT OF PARTICIPANTS

4.1 Patients

Specific **inclusion criteria** are:

- Planned hip or knee surgery (either for fracture or periprosthetic revision), or lung surgery
- Age ≥ 60
- Ambulatory at baseline.

FEAT Study Protocol

- Expected duration of surgery > 90 minutes

Specific exclusion criteria

- Planned concurrent surgery
- Allergy to adhesive tape
- Short Blessed Test score >20
- Clinical diagnosis of dementia
- Opinion of either the anesthesiologist or surgeon that the patient is not appropriate.

Because of the age of these patients, it is anticipated that they will suffer from chronic diseases common in the elderly. However, each patient will be healthy enough to undergo the proposed operation, as judged by both the surgical and anesthesia services according to usual clinical practice.

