5.4 Description of Intervention and Control

The critical difference will be blood pressure targets during surgery. Cerebral autoregulation monitoring will begin prior to anesthesia induction, with the LLA and/or ULA anticipated to be available within 30 minutes. The methods are described in the subsequent section “Intraoperative Monitoring of Cerebral Autoregulation.” These values will be used to establish blood pressure targets.

In the intervention group, at 30 minutes after the start of monitoring, [name] will visualize the autoregulation curves. Upon confirmation of an adequate curve, a blood pressure target will be provided to the anesthesiologist. [name] will visualize the autoregulation curves every 30-60 minutes to update the blood pressure target as necessary. The lower limit of autoregulation will not be <55 mm Hg. or >90 mm Hg.

In the intervention arm, the anesthesia provider will target MAP>LLA with the following strategy: reduce anesthetic agent while maintaining adequate anesthetic depth as clinically determined, IV fluid administration, and vasopressor infusion (likely dopamine or levophed, but at the discretion of the anesthesiologist). MAP<ULA will be targeted with the following strategy: vasodilator infusion (likely nicardipine or nitroglycerine, but at the discretion of the anesthesiologist) or other clinical approaches as decided by the anesthesiologist. If the treating anesthesiologist or surgeon feels that the blood pressure target is too high or too low for clinical reasons, then they will request a different target, and this request will take priority. In the control arm, the anesthesia provider will use usual care guidelines, which is generally systolic blood pressure >90 mm Hg.

FEAT Study Protocol

Patients will be allowed to be enrolled in other studies. Adherence will be assessed as part of the feasibility outcomes.

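### The protocol prints small 2:1 blocks of 3 or 6, so anyone who knew a stratum's earlier allocations could predict about 30% of next assignments with at least 90% confidence; withholding and enlarging the sizes costs almost nothing

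*Combined protocol and SAP*

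**What the plan says.** - Section 5.3: "Randomization will be 2:1 in intervention vs. standard arm", with "stratification by orthopedic vs. lung surgery", in "permuted blocks of 3 or 6". Section 3.1 gives the same scheme. How the two sizes are mixed is not stated.
- Section 3.1 on size: "We will enroll 25 patients with usable data". Section 5.3 adds that "each surgical strata will have the opportunity for 17 intervention patients and 8 control patients to be enrolled".
- Section 5.3 on concealment: randomization occurs on entry to the operating room, when "the anesthesiologist is handed a sealed opaque envelope indicating the study allocation".
- Section 5.4, intervention arm only: a study role inspects the curves, and "Upon confirmation of an adequate curve, a blood pressure target will be provided to the anesthesiologist".
- Section 4.1 allows exclusion on "Opinion of either the anesthesiologist or surgeon that the patient is not appropriate". Section 5.2.1 makes the approach to a patient depend on research staff being free to monitor the case.
- Section 3.1 calls the trial double-masked, but no section names the masked roles. Section 8.3 describes weekly team meetings that cover the whole study.

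**The concern.** A sealed envelope hides the current allocation. It does not hide one that can be worked out from earlier allocations in the same stratum when the block sizes are known. The smallest block holds only two intervention places and one control place, so once its control has appeared the rest of that block is fixed.

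The arm is known in the operating room, and judgement about who enters the trial continues until the patient arrives there. If someone exercising that judgement expects intervention next, a particular patient could be held back or judged unsuitable. The comparisons at risk are the between-arm ones in section 7.2: delirium, cognition and function, plus any reading of bleeding or ischemia against the other arm. With 8 controls, one patient's delirium status moves the control rate by 1/8 = 12.5 points. At the 20% incidence that section 2 gives as the upper end, only 8 × 0.20 = 1.6 control events are expected.

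**Working it through.** **Inputs from the plan.** Ratio 2:1; block sizes 3 and 6; two strata; 25 patients in total.

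**Assumptions, because the plan is silent.** Equal mix of the two sizes in random order; stratum splits of 25/0, 20/5, 17/8 and 13/12; an observer who knows the sizes and all earlier allocations in the stratum. The mix and the share of history seen are then varied.

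**1. The plan's own figure.** 25 × 2/3 = 16.7 and 25 × 1/3 = 8.3, which gives 17:8 as stated. The plan gives no predictability figure.

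**2. Single block sizes, by hand.** In a block with *a* intervention and *c* control places, the next assignment is certain once one arm is used up. The expected number of certain places is a/(c+1) + c/(a+1).
- Size 3: 2/2 + 1/3 = 1.33. One stratum of 25 holds 8 whole blocks: 8 × 1.33 / 25 = 43%.
- Size 6: 4/3 + 2/5 = 1.73. Four whole blocks: 4 × 1.73 / 25 = 28%.

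These agree with the simulated 40-43% (all 3) and 24-28% (all 6).

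**3. Mixed sizes, one step by hand.** Suppose the first patient in a stratum is a control. Both sizes make that equally likely (1/3), so their weights are unchanged. The chance of intervention next is 1 for size 3 and 4/5 for size 6.
- Equal mix: (1 + 0.80)/2 = 0.90.
- Two-thirds blocks of 3: 0.933.
- One-third blocks of 3: 0.867.

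The share above a 90% cut-off therefore depends on the mix.

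**4. Whole trial.** The probability of the next arm was updated exactly by Bayes' rule after each allocation, over simulated trials.

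| Scenario (blocks 3/6) | Share at least 90% predictable |
|---|---|
| Equal mix, full history | 28-32% |
| Two-thirds blocks of 3 | 33-35% |
| One-third blocks of 3 | 20-24% |
| All 6 / all 3 | 24-28% / 40-43% |
| Equal mix, 75% of history seen | 17-18% |
| Equal mix, 50% of history seen | 8-9% |

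Under the equal mix with full history, 8-10% of assignments are certain. About 28-30% are predictable as intervention and about 2% as control (0.02 × 25 = 0.5 of a patient).

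**5. Larger sets, sizes still known.** Equal mix of 3/6/9: 11-13%. Equal mix of 6/9: 13-15%. In the step 3 example, 3/6/9 gives (1 + 0.80 + 0.75)/3 = 0.85, so part of the gain is cases slipping just below the cut-off. Best-guess accuracy shows this: 74.8% for 3/6 and 72.6% for 3/6/9, against 66.7% from always guessing intervention. The excess over that baseline falls from 8.1 to 5.9 points.

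**6. Sizes withheld.** An observer unsure among 3, 6, 9 and 12 is at least 90% confident for about 1-5% of assignments. In the step 3 example, that observer's probability is (1 + 0.80 + 0.75 + 8/11)/4 = 0.82.

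**7. Cost in precision (13/12 split).** The SD of the control count rises from 0.62 to 0.79 with 3/6/9. The mean of 1/n₁ + 1/n₂ goes from 0.1807 to 0.1809, and 0.0002/0.1807 = 0.1%. A separate simulation of the mean standard error gives relative values of 0.9914 and 0.9924 for the same split; (0.9924/0.9914)² − 1 = 0.2%.

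**The case against.** The strongest objection concerns who knows what. A reader might infer that staff see every allocation. The documents do not say so. Section 5.3 shows each treating anesthesiologist learning the arm of that case, and section 5.4 implies the same for the curve-reading role. Nothing shows that a person who screens, consents or judges suitability holds the full sequence, or that the same anesthesiologist recurs. This stands, so the 30% must remain conditional. It does not dispose of the point, because the plan describes no barrier either and the double-masked label is attached to no role.

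Second, confident predictions are almost all of intervention under the equal mix, so steering a patient into control is rarely possible. That stands. The remaining route is leaving a patient out when intervention is expected, and doing so often would work against the plan's own recruitment criterion of more than 60%.

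Third, most feasibility criteria in section 7.1 are not between-arm comparisons, and the efficacy comparisons are exploratory. That stands and limits the severity. Section 7.2 nevertheless uses the between-group differences to help judge whether a further trial is worthwhile.

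Fourth, withholding the sizes might make larger blocks unnecessary. This is partly right, since withholding does much of the work. But the present sizes are already in print, so withholding them unchanged does little against anyone who has read this text.

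**Conclusion.** The point holds as a conditional weakness and a cheap improvement. If one person involved in screening or eligibility knew all earlier allocations in a stratum, about 30% of next assignments would be at least 90% predictable under an equal mix. The range is 20-43% across mixes, and the share drops to 8-9% when half the history is seen.

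Three stronger readings are not supported. The documents do not establish that anyone in a recruiting role has that history, so this is no evidence that allocation is compromised. The large reduction from bigger blocks belongs to the 90% measure: best-guess accuracy falls only about 2 points (about 75% to 73%), so predictability as a whole is not halved. Silence on who prepares the envelopes is missing detail and not a demonstrated flaw.

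The exposure is to the exploratory delirium, cognition and function comparisons and to any between-arm reading of safety. Feasibility criteria that involve no comparison of arms are not the target of this concern.

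**What to change.** In sections 3.1 and 5.3, replace the printed sizes with a statement that allocation uses randomly varying block sizes within stratum, held in a restricted document. In that document, draw the sizes from a larger set such as 3, 6 and 9. Describe the per-stratum 17 and 8 as approximate. As useful clarification, state which roles are masked and who prepares and holds the list and envelopes, preferably someone outside screening, consent and operating-room monitoring.

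The cost is a new list and a few sentences. The statistical downside is an SD of the control count of about 0.8 in place of about 0.6-0.7, and about 0.1-0.2% more variance for a between-group mean. The change protects only allocations made after it takes effect, so it is best made before enrollment.

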5.4 Description of Intervention and Control

The critical difference will be blood pressure targets during surgery. Cerebral autoregulation monitoring will begin prior to anesthesia induction, with the LLA and/or ULA anticipated to be available within 30 minutes. The methods are described in the subsequent section “Intraoperative Monitoring of Cerebral Autoregulation.” These values will be used to establish blood pressure targets.

In the intervention group, at 30 minutes after the start of monitoring, [name] will visualize the autoregulation curves. Upon confirmation of an adequate curve, a blood pressure target will be provided to the anesthesiologist. [name] will visualize the autoregulation curves every 30-60 minutes to update the blood pressure target as necessary. The lower limit of autoregulation will not be <55 mm Hg. or >90 mm Hg.

In the intervention arm, the anesthesia provider will target MAP>LLA with the following strategy: reduce anesthetic agent while maintaining adequate anesthetic depth as clinically determined, IV fluid administration, and vasopressor infusion (likely dopamine or levophed, but at the discretion of the anesthesiologist). MAP<ULA will be targeted with the following strategy: vasodilator infusion (likely nicardipine or nitroglycerine, but at the discretion of the anesthesiologist) or other clinical approaches as decided by the anesthesiologist. If the treating anesthesiologist or surgeon feels that the blood pressure target is too high or too low for clinical reasons, then they will request a different target, and this request will take priority. In the control arm, the anesthesia provider will use usual care guidelines, which is generally systolic blood pressure >90 mm Hg.

FEAT Study Protocol

Patients will be allowed to be enrolled in other studies. Adherence will be assessed as part of the feasibility outcomes.

6 SAFETY ASSESSMENTS

6.1 Adverse Events and Serious Adverse Events

Adverse events (AE) encountered during or after surgery are recorded on the appropriate AE section of the CRF. Adverse events are defined as any untoward or unfavorable medical occurrence in a human study, including any abnormal sign (for example, abnormal physical exam or laboratory finding), symptom, or disease, temporally associated with the participants' involvement in the research, whether or not considered related to the participant's participation in the research.

Serious adverse events (SAE) are a subset of AE that meet one of the following criteria:

- Results in death
- Is life threatening
- Places the participant at immediate risk of death from the event as it occurred
- Requires or prolongs hospitalization substantially
- Causes persistent or significant disability or incapacity
- Is another condition which investigators judge to represent significant hazards

Severity Classification

Classifications of adverse events include the following:

- **Mild:** Awareness of signs or symptoms, but easily tolerated and are of minor irritant type causing no loss of time from normal activities. Symptoms do not require therapy or a medical evaluation; signs and symptoms are transient.
- **Moderate:** Events introduce a low level of inconvenience or concern to the participant and may interfere with daily activities, but are usually improved by simple therapeutic measures; moderate experiences may cause some interference with functioning
- **Severe:** Events interrupt the participant's normal daily activities and generally require systemic drug therapy or other treatment; they are usually incapacitating

Expectedness of Adverse Events

AEs will be assessed as to whether they were expected to occur or unexpected, meaning not anticipated based on current knowledge found in the protocol, investigator brochure, product insert, or label. Categories are:

- **Unexpected** - nature or severity of the event is not consistent with information about the condition under study or intervention in the protocol, consent form, product brochure, or investigator brochure.
- **Expected** - event is known to be associated with the intervention or condition under study.

Relatedness of Adverse Events

The potential event relationship to the study intervention and/or participation is assessed by the site investigator. A comprehensive scale in common use to categorize an event is:

- **Definitely Related:** The adverse event is clearly related to the investigational agent/procedure – i.e. an event that follows a reasonable temporal sequence from administration of the study intervention, follows a known or expected response pattern to the suspected intervention, that is

FEAT Study Protocol

confirmed by improvement on stopping and reappearance of the event on repeated exposure and that could not be reasonably explained by the known characteristics of the subject's clinical state.

- **Possibly Related:** An adverse event that follows a reasonable temporal sequence from administration of the study intervention follows a known or expected response pattern to the suspected intervention, but that could readily have been produced by a number of other factors.
- **Not Related:** The adverse event is clearly not related to the investigational agent/procedure - i.e. another cause of the event is most plausible; and/or a clinically plausible temporal sequence is inconsistent with the onset of the event and the study intervention and/or a causal relationship is considered biologically implausible.

